12.0 HEALTH OUTCOMES ANALYSES

Not applicable.

13.0 INTERIM ANALYSIS

The interim analysis will be conducted when at least 50% of randomized patients have either completed or discontinued the study. A futility analysis and safety analysis will be included in the interim analysis listed in the Appendix III. The general data derivation and preparation will follow the specification in the SAP and the amendment.

The futility assessment of the primary efficacy parameter (CDRS-R total score) on ITT population will be based on the conditional power as described in Lan et al. (1988) and Proschan et al. (2006). In calculating the conditional power, it is assumed that the future patients to be enrolled into the Study will have similar efficacy as those of the existing patients of the same treatment group. The non-binding futility criteria will be met when the conditional power for detecting a statistically significant treatment difference between the levomilnacipran treatment group (40-80 mg/day) and placebo at the final analysis given the interim analysis results is 0.2 (20%) or lower. Further details of the calculation of conditional power are provided in Appendix IV.

The safety analysis will be performed on the Safety Population, including the summary of TEAE, SAE, death, and TEAE leading to study discontinuation; the incidence of common TEAEs (≥ 2%); PCS for laboratory parameters, vital signs, and ECGs; and the summary of C-SSRS during the double-blind treatment period.

Data will be presented in an unblinded fashion. A separate, independent, fire-walled Statistical Analysis Group and Data Review Committee will be established to conduct the unblinded interim analysis, review the unblinded results and make recommendations regarding the continuation of the study. To maintain the scientific reliability of statistical analyses after the final database lock, preserve the integrity of study conduct, and guard from introducing any potential bias into the conduct of the study and/or analysis of its results, individuals in these two groups will not be involved in any operational aspects of the trial.

14.0 DETERMINATION OF SAMPLE SIZE

The effect size (treatment group difference relative to pooled SD) of 0.36 for both levomilnacipran and fluoxetine is based on a treatment difference of 4 units with a common pooled SD of 11.1 for the primary efficacy parameter, change from baseline to Week 8 in CDRS-R total score. A sample size of 480 patients (160 per treatment group) will be needed to provide 85% power for primary analysis (levomilnacipran vs. placebo) based on an MMRM model using simulation method (Lu, 2012). The simulation assumed a correlation of 0.7 between the repeated measures and a dropout rate of 17% based on historical data in pediatric patients.

15.0 STATISTICAL SOFTWARE

Statistical analyses will be performed using version 9.4 (or newer) of SAS on a Linux operating system.

16.0 DATA HANDLING CONVENTIONS

16.1 VISIT TIME WINDOWS

Table 16–1 and Table 16–2 present the visits assigned for efficacy and safety analyses and the corresponding range of treatment days (window) during which an actual visit may occur.

Table 16–1. Visit Time Windows for Double-Blind Treatment Period

Derived Visit	Scheduled Visit Daya	Window
Baseline	Week 0 (Day 1)	Days ≤ 1
Week 1	End of Week 1 (Day 8)	Days [2, 11]
Week 2	End of Week 2 (Day 15)	Days [12, 18]
Week 3	End of Week 3 (Day 22)	Days [19, 25]
Week 4	End of Week 4 (Day 29)	Days [26, 35]
Week 6	End of Week 6 (Day 43)	Days [36, 49]
Week 8	End of Week 8 (Day 57)	Days ≥ 50 days and within double-blind treatment period
End of double-blind treatment period ^b	Final or Termination Visit	during the double-blind treatment period

a Relative to the date of the first dose of double-blind investigational product. Day 1 = the date of the first dose of double-blind investigational product. There is no Day 0 or Week 0.

Table 16–2. Visit Time Windows for the Double-Blind Down-Taper period

Derived Visit	Scheduled Visit	Window
Week 9	End of Week 9	Within the double-blind down-taper period (from 1 day after the end of double-blind treatment period to the end of the double-blind down-taper period)
End of double-blind down-taper period ^a	Final of termination visit during the double-blind down-taper period.	

a Presented in analysis tables for safety parameters collected during the double-blind-down-taper period. If any assessments are repeated at the end-of-double-blind-down-taper-period visit, the algorithm in Section 16.4 will be used to determine which values are used in the analysis.

b Presented in analysis tables for safety parameters, including but not limited to electrocardiograms, clinical laboratory values, and vital signs, and C-SSRS. If repeat assessments occur at the end of double-blind treatment period visit, the algorithm in Section 16.4 will be used to determine which values are used in the analysis.

If the visit date is on or after the date of the first dose of double-blind investigational product, the study day is calculated by visit date – date of the first dose of double-blind investigational product +1. If the visit date is before the date of the first dose of double-blind investigational product, the study day is calculated by visit date – date of the first dose of double-blind investigational product. Therefore, a negative day indicates a day before the start of the double-blind investigational product.

If a patient has 2 or more visits within the same window, the last visit with a nonmissing value will be used for analysis.

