Inclusion and exclusion criteria	X	X								
Determination of ability to swallow capsule		X								
Medical history	X									
Psychiatric history	X									
Medication history and nondrug psychiatric treatment history		X	X							
Concomitant medications			X	X	X	X	X	X	X	
Physical examination	X ^e								X	
Clinical laboratory determinations	X ^e								X	
Serum β-hCG pregnancy test ^f	X ^e								X	
Thyroxine, TSH tests	X ^e									
Urine drug screen	X ^e									
ECG	X ^e				X			X		
Vital signs (BP, pulse, weight)		X	X	X	X	X	X		X	
Vital signs (BP, pulse, weight and height ^g)	X ^e								X	
K-SADS-PL ^h	X									

SCHEDULE OF EVALUATIONS: Study LVM-MD-14										
	Screening Period	Double-blind Treatment Period							Double-blind Down-taper Period	
		Visit 1^a	Visit 2 (Baseline)	Visit 3	Visit 4	Visit 5	Visit 6	Visit 7	Visit 8/ ET^b	
End of Study Week	-1	0	1	2	3	4	6	8	9	
CDRS-R	X	X	X	X	X	X	X	X		
CGI-S	X	X	X	X	X	X	X	X		
CGI-I			X	X	X	X	X	X		
C-SSRS	X	X	X	X	X	X	X	X	X	
PK Sampling ⁱ					X	X	X			
AEs	X	X	X	X	X	X	X	X	X	
IP dispensing			X	X	X	X	X	X ^j		
IP return				X	X	X	X	X	X ^j	
IP compliance			X	X	X	X	X	X	X ^j	

Note: If necessary, visits may be conducted up to 3 days before or after scheduled visits relative to the Baseline Visit (Visit 2).

- a After assent and consent are obtained, the screening period may be up to 5 weeks in duration, as described in Section 9.5.5.
- b Visit 8 assessments to be completed for all randomized patients who complete the study or discontinue before Week 8.
- c All randomized patients must complete Visit 8/ET and, at the end of the down-taper period, return for Visit 9/SFU. Patients who do not enter the down-taper period must return for Visit 9/SFU approximately 1 week after Visit 8/ET Visit.
- d If the parent(s), guardian, or legally authorized representative (LAR) is also the patient's caregiver, he/she will be asked to sign both the parent and caregiver consents.
- e May be repeated at the Investigator's discretion before Visit 2.
- f A pregnancy test will be obtained for female patients of childbearing potential only.
- g Height will be recorded at Screening (Visit 1) and Visit 8/ET using a stadiometer.
- h K-SADS-PL data will be retained as source documents at the site.

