9.4.5 Selection and Timing of Dose for Each Patient

All investigational products should be taken orally as a single dose, once-daily at the same time each day. After consent/assent is obtained, patients undergoing screening will be required to swallow a placebo capsule to confirm their ability to swallow the investigational product, as part of their eligibility assessment.

Patients who meet all eligibility criteria at Visit 1 (Screening) and who continue to meet all the eligibility criteria for participation in the study will be assigned a randomization number at Visit 2 (Baseline) and dispensed the corresponding blister card containing capsules of double-blind investigational product for Week 1. Patients will begin dosing with double-blind capsules on the next day. Patients will be instructed to take 2 capsules orally as a single dose, once daily at approximately the same time each day (morning dosing recommended), with or without food.

Dosing may be switched from the morning to another time of day if a patient prefers or if tolerability issues arise. However, any switch must allow at least 20 hours between 2 consecutive doses.

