9.4.5.2 Double-blind Treatment Period

The titration schedule is as follows:

- Levomilnacipran: Days 1-3, 10 mg/day; Days 4-7, 20 mg/day; Week 2 through Week 8, 40 mg/day; Based on therapeutic response and tolerability, an additional dose increase to 80 mg/day is permitted at Week 3.
- Fluoxetine 20 mg/day (active comparator): Week 1, 10 mg/day; Week 2 through Week 8, 20 mg/day

Patients will be assigned a randomization number at Visit 2 (Baseline) and dispensed the corresponding blister card containing capsules of double-blind investigational product for Week 1. Patients will begin dosing with double-blind capsules on the next morning. Patients will be instructed to take 2 capsules from each column (1 each from Row A and Row B) as a single dose daily each morning with or without food. The double-blind dosing regimen is presented in [Table 9-1](#).

Table 9-1.

Double-blind Dosing Regimen

Treatment Group	Row	Week					
		1		2	3-8	Down-Taper	
		Days 1-3	Days 4-7	Days 1-7	Days 1-7	Days 1-2	Days 3-7
Levomilnacipran 40 mg - 80 mg	A	LVM 10 mg	LVM 20 mg	LVM 40 mg	LVM 40 mg	LVM 40 mg	LVM 20 mg
	B	Placebo	Placebo	Placebo	Placebo	Placebo	Placebo
	A	Optional dose escalation to 80 mg as determined by treating physician			LVM 40 mg	LVM 40 mg	LVM 20 mg
	B				LVM 40 mg	Placebo	Placebo
Fluoxetine 20 mg	A	Fluoxetine 10 mg	Fluoxetine 10 mg	Fluoxetine 20 mg	Fluoxetine 20 mg	Fluoxetine 10 mg	Fluoxetine 10 mg
	B	Placebo	Placebo	Placebo	Placebo	Placebo	Placebo
Placebo	A	Placebo	Placebo	Placebo	Placebo	Placebo	Placebo
	B	Placebo	Placebo	Placebo	Placebo	Placebo	Placebo

ET = Early termination; LVM = levomilnacipran.

Patients will be instructed to return the blister card with any remaining investigational product, and to return it even if it is empty, preferably at the next study visit. Additional investigational product will be dispensed as per the schedule shown in Section 2.0.

If a patient experiences an AE, the investigational product may be stopped for up to a maximum of 4 consecutive days. The date and reason for missed doses must be recorded on the appropriate page of the eCRF. If appropriate, as deemed by the investigator, patient may resume medication at 40 mg/day or reduce to 40 mg/day (if taking 80 mg/day). Those unable to tolerate 40 mg/day should be discontinued from the study.

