9.5.5 Schedule of Assessments

The schedule of study procedures and assessments is tabulated by visit in the [Schedule of Evaluations](#) in Section 2.0 and Section 2.1. The descriptions of the procedures to be performed at each visit are provided below.

The screening period should be 1 week (\pm 3 days) before Visit 2, but may be extended up to a total of 5 weeks to accommodate prior medication washout or to repeat assessments. The reason for the extended screening will be recorded in the source documents.

If necessary, visits may be conducted up to 3 days before or after the indicated postbaseline weeks relative to Visit 2 (Baseline).

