Vital signs (BP, pulse, weight)		X	X	X	X	X	X		X
Vital signs (BP, pulse, weight and height ^g)	Xe							X	
K-SADS-PL ^h	X								
CDRS-R	X	X	X	X	X	X	X	X	
CGI-S	X	X	X	X	X	X	X	X	
CGI-I			X	X	X	X	X	X	
C-SSRS	X	X	X	X	X	X	X	X	X
PK sampling ⁱ					X	X	X		
AEs	X	X	X	X	X	X	X	X	X
IP dispensing		X	X	X	X	X	X	X ^j	-
IP return			X	X	X	X	X	X	X ^j
IP compliance			X	X	X	X	X	X	\mathbf{X}^{j}

Note: If necessary, visits may be conducted up to 3 days before or after scheduled visits relative to the Baseline Visit (Visit 2).

a After assent and consent are obtained, the screening period may be up to 5 weeks in duration.

an PLC Page 9

- b Visit 8 assessments to be completed for all randomized patients who complete the study or discontinue before Week 8
- c All randomized patients must complete Visit 8/ET and, at the end of the down-taper period, return for Visit 9/SFU. Patients who do not enter the down-taper period must return for Visit 9/SFU approximately 1 week after Visit 8/ET Visit.
- d If the parent(s), guardian, or legally authorized representative (LAR) is also the patient's caregiver, he/she will be asked to sign both the parent and caregiver consents.
- e May be repeated at the Investigator's discretion before Visit 2.
- f A pregnancy test will be obtained for female patients of childbearing potential only.
- g Height will be recorded at Screening (Visit 1) and Visit 8/ET using a stadiometer.
- h K-SADS-PL data will be retained as source documents at the site.
- i *PK only collected on patients aged 7-11 years.* Sparse PK blood samples will be collected during Visit 5 (at predose and 1-4 hour postdose), Visit 6 (4-6 hours postdose), and Visit 7 (6-8 hours postdose). At Visit 5, or at any 24-hour period between Visit 5 and Visit 7, inclusive, serial blood samples will be collected from a subset of consented 7-11-year-old patients instead of sparse PK samples at the following time points: predose [20-24 hours after the most recent dose], and 2, 4, 6, 8, 10-12, and 24-hours postdose.
- For patients entering the double-blind down-taper period.

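### SAP Table 16-1 assumes first dose on the Visit 2 date; with the protocol's next-day dosing, Visits 4, 5 and 6 held exactly 3 days early are assigned to the previous week

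*SAP*

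**What the plan says.** **The analysis clock.** Footnote a of SAP Table 16-1 counts days "Relative to the date of the first dose of double-blind investigational product" and makes that date Day 1. The table places Baseline on Day 1 as well, and lists later visits in the style "End of Week 2 (Day 15"). The windows are Week 1 [2,11], Week 2 [12,18], Week 3 [19,25], Week 4 [26,35], Week 6 [36,49] and Week 8 from Day 50. If two visits share a window, "the last visit with a nonmissing value will be used for analysis".

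**The visit clock.** Protocol 9.5.5 says that, if necessary, "visits may be conducted up to 3 days before or after the indicated postbaseline weeks relative to Visit 2 (Baseline"). The note to the SAP's own schedule (Table 4-2) likewise ties the 3-day tolerance to Visit 2.

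**The dosing start.** After dispensing at Visit 2, Protocol 9.4.5 says "Patients will begin dosing with double-blind capsules on the next day"; Section 9.4.5.2 says "Patients will begin dosing with double-blind capsules on the next morning".

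SAP 18.0 lists no changes from the protocol, and nothing in the SAP adjusts for the one-day gap between Visit 2 and first dose.

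**The concern.** The table uses one origin (first dose) while the visits it sorts are scheduled from another (Visit 2), and the protocol puts these one day apart. The Week 2 and Week 3 windows are exactly the listed day plus or minus 3, and Week 4 opens exactly 3 days before its listed day. Those lower bounds have no slack, so a one-day shift pushes some permitted visits into the week before.

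The consequences are:

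- **Observed-case analyses.** The early visit replaces any earlier nonmissing value in the window it lands in, and its own week is left empty unless a later visit happens to fall there.
- **LOCF.** Under SAP 16.2 the emptied week is refilled with the early visit's own value, so what is lost is the preceding visit's value.
- **Results affected.** These are the by-visit CDRS-R, CGI-S, CGI-I, response and remission results, and the descriptive vital-sign and ECG tables, at Weeks 1 to 4. For instance, a Visit 5 ECG on Day 18 would be tabulated under Week 2, when Protocol 9.5.2.11 schedules no ECG.

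**Working it through.** **Inputs.** Visit targets are 7, 14, 21, 28, 42 and 56 days after Visit 2 (Visits 3 to 8), each with offsets of -3 to +3 days (Protocol 9.5.5). That gives 6 × 7 = 42 permitted visit-day combinations. Windows and day formula come from SAP 16.1.

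**Formula.** Let k be days from Visit 2 to the visit and g be days from Visit 2 to first dose. Study day = k − g + 1 if k ≥ g, otherwise k − g (there is no Day 0).

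**Reproducing the table (g = 0).** The scheduled days are 7+1, 14+1, 21+1, 28+1, 42+1 and 56+1, that is 8, 15, 22, 29, 43 and 57, exactly as listed. All 42 combinations fall in their own windows.

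**Protocol dosing (g = 1).** Visit 2 becomes Day -1 and study day equals k, so the scheduled days are 7, 14, 21, 28, 42 and 56.

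| Visit | Permitted days | Own window | Outside it |
|---|---|---|---|
| 3 | 4–10 | Week 1 [2,11] | none |
| 4 | 11–17 | Week 2 [12,18] | Day 11, goes to Week 1 |
| 5 | 18–24 | Week 3 [19,25] | Day 18, goes to Week 2 |
| 6 | 25–31 | Week 4 [26,35] | Day 25, goes to Week 3 |
| 7 | 39–45 | Week 6 [36,49] | none |
| 8 | 53–59 | Week 8 (≥ 50) | none |

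Three of 42 are misassigned: one of seven offsets for each of Visits 4, 5 and 6.

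**What such a visit displaces**, with the neighbouring visit within tolerance:

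- Visit 4 on Day 11 shares [2,11] with Visit 3 on any of Days 4–10: 7 of 7.
- Visit 5 on Day 18 shares [12,18] with Visit 4 on Days 12–17: 6 of 7.
- Visit 6 on Day 25 shares [19,25] with Visit 5 on Days 19–24: 6 of 7.

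Total: 7 + 6 + 6 = 19 of 21.

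**Whether the next scheduled visit fills the emptied week:**

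- Week 2 stays unfilled unless Visit 5 is on Day 18: 6 of 7.
- Week 3 stays unfilled unless Visit 6 is on Day 25: 6 of 7.
- Week 4 is never filled by Visit 7 (Days 39–45): 7 of 7.

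Total unfilled: again 19 of 21. An unscheduled visit on Days 12–18, 19–25 or 26–35 could still fill Week 2, 3 or 4. So could an early-termination visit, since footnote b of the protocol schedule has "Visit 8 assessments to be completed for all randomized patients who complete the study or discontinue before Week 8".

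**Longer gaps.** Protocol 9.5.5.2 allows a remote Visit 2 with courier supply but gives no delivery time, so any gap above one day is an assumption. The table as written misassigns 6 of 42 at g = 2 and 9 of 42 at g = 3 (Visits 4 to 6 only in both cases).

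**The case against.** The best defence is that Table 16-1 defines derived visits by time on treatment. Week 1 dosing is Days 1–7, so Day 8 is a natural end of Week 1. Every cut-off is the midpoint between adjacent listed days (8 and 15 give 11.5; 15 and 22 give 18.5; 22 and 29 give 25.5). Day 11 is 3 days from Day 8 and 4 from Day 15, so it goes to the nearer target. On this view nothing is misfiled, and the choice of clock is a design decision.

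That does not rescue the table. Its day column claims to give the scheduled visit days, and each is one day later than the protocol's schedule allows under the protocol's own dosing rule. Midpoints between the actual days (7, 14, 21, 28) are 10.5, 17.5 and 24.5, which would put Days 11, 18 and 25 in the correct weeks. The midpoint argument therefore supports moving the boundaries.

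Several points do stand:

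- Baseline is handled correctly, because its window is Day 1 or earlier and SAP 10.0 takes the last value at or before first dose.
- Only one extreme offset is affected, at three intermediate visits, and the tolerance is meant for use when necessary.
- PCS counts and worst C-SSRS ratings use all postbaseline assessments (SAP 16.4) and are untouched.
- The 19 of 21 figures are conditional on a visit already being 3 days early, and weight all calendars equally.

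**Conclusion.** The point holds and is minor. Following the SAP exactly, with dosing as the protocol describes, assigns 3 of 42 permitted visit-day combinations to the wrong week and can drop a valid earlier value. With first dose on the Visit 2 date the count is 0 of 42, which isolates the origin of the day count as the cause.

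Permitted Visit 8 dates stay in the Week 8 window, so Week 8 CDRS-R and CGI-S values do not move. The primary MMRM is affected only through relabelled or lost intermediate values, by an amount that cannot be computed from the documents.

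The counts assume that first dose is the day after Visit 2 and that visits are within tolerance. They are calendar combinations, not patient rates; the documents do not say how often visits occur exactly 3 days early.

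**What to change.** Amend SAP 16.1 before the final unblinding, so that the change cannot appear data-driven. Either edit works under the protocol's dosing rule.

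**(a) Count postbaseline window days from Visit 2 (Visit 2 = Day 1) and leave the windows as they are.** First dose stays the origin for baseline, exposure and TEAEs. The visit ranges become Days 5–11, 12–18, 19–25, 26–32, 40–46 and 54–60, with 0 of 42 misassigned whether dosing starts the same day or the next day, and up to a 3-day gap. At an assumed 4-day gap 1 of 42 fails, because Visit 3 at -3 days falls on the first-dose date; at 5 days 2 of 42 fail.

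**(b) Keep the first-dose clock and move the table one day earlier.** Scheduled days become 7, 14, 21, 28, 42 and 56. The windows become Week 1 [2,10], Week 2 [11,17], Week 3 [18,24], Week 4 [25,34], Week 6 [35,48] and Week 8 from Day 49. This also gives 0 of 42 under next-day dosing, but 3 of 42 if first dose is on the Visit 2 date and 3 of 42 at a 2-day gap.

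In both, an assessment on or before the first-dose date stays baseline and is never postbaseline. Option (a) is the sturdier.

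The cost is small: a second day count for (a) or an edited table for (b), plus re-validation of the windowing program. Under (a), visit labels follow time since Visit 2 rather than time on drug, a one-day difference under the protocol's dosing rule.

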16.2 DERIVED EFFICACY VARIABLES

If a patient misses a postbaseline visit or if his/her postbaseline visit is outside of the visit time window, a record for the scheduled visit will be imputed using the last observed nonmissing value immediately before the missing value. If the missing value occurs at Week 1, the baseline value will be carried forward for Week 1, provided that at least 1 subsequent postbaseline assessment is available. For a composite scale such as CDRS-R total score, individual items of the rating scale will not be carried forward. Only total scores will be carried forward using the LOCF approach.

16.3 AGE-AND-GENDER-CORRELATED VALUES FOR WEIGHT AND HEIGHT

To adjust weight (kg) and height (cm) for sex and age, one needs to compare them to standard reference values for the same sex and age group, which are available in the United States Growth Charts and can be downloaded from: http://www.cdc.gov/growthcharts/percentile_data_files.htm.

The z-score is calculated as below

$$z = \frac{(X/M)^L - 1}{SL}$$
, if L \neq 0 and

$$z = \frac{\ln(X/M)}{S}$$
, if $L = 0$,

where X is the physical measurement (e.g. weight and height) and L, M and S are the values from the appropriate table corresponding to the age in months (or length/stature) and sex (1 = male; 2 = female). X must be in metric measurements (kilograms or meters). This is called LMS method (Cole TJ, 1990), and parameters L, M, and S are the Box-Cox transformation power, median, and standard deviation, respectively, in the reference data, which again are provided in the reference data tables.

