For the C-SSRS, the number and percentage of patients with suicidal ideation or suicidal behavior as recorded on the C-SSRS scale will be presented by treatment group. The distribution of responses for most severe suicidal ideation and suicidal behavior during the lifetime history, the double-blind treatment period and the down-taper period will also be presented by treatment group for the Safety Population. Supportive listings will be provided and will include the PID number, treatment group, visit number, lifetime history, and postbaseline values for each patient. Intensity of ideation, suicidal behavior type, and lethality of suicidal behavior will also be included in these listings.

9.7.6.5.2 *Growth Evaluation*

Weight and height will be presented as standardized z-scores adjusted for gender and age, using the lambda-mu-sigma method ([Cole TJ 1990](#)). To assess the impact of treatment on growth, the change from baseline in the age and gender adjusted height will be analyzed using an analysis of variance model with treatment as factor. A non-parametric (Wilcoxon) test will also be performed.

9.7.6.6 *Investigational Product Plasma Concentration Parameters*

Plasma samples will be analyzed for the concentrations of levomilnacipran using validated bioanalytical methods. Population PK parameters will be estimated using nonlinear mixed-effects modeling methods. The study will be prospectively powered to target a 95% confidence interval within 60% and 140% of the geometric mean estimates of clearance and volume of distribution for levomilnacipran ER, with at least 80% power.

9.7.7 *Health Economics and Outcomes Research Analyses*

Not applicable.

9.7.8 *Interim Analysis*

The interim analysis was conducted to identify early signs of futility after 62% of randomized patients had either completed or discontinued the study. The futility assessment of the primary efficacy parameter (CDRS-R total score) on ITT population was based on the conditional power as described in [Lan et al. 1999](#). In calculating the conditional power, it was assumed that the future patients to be enrolled into the Study will have similar efficacy as those of the existing patients of the same treatment group. The non-binding futility criteria was set when the conditional power for detecting a statistically significant treatment difference between the levomilnacipran treatment group

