11.5.2 Growth Evaluation

Weight and height will be presented as standardized z-scores adjusted for gender and age, using the LMS method (Cole T.J., 1990).

To assess the impact of treatment on growth, the change from baseline to Week 8 in the age-and-gender-adjusted height and weight will be analyzed using an ANOVA model with treatment as factor. A non-parametric (Wilcoxon) test will also be performed.

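### SAP 16.3 gives two units for height: metres set against a reference median in centimetres would make height z-scores impossible and distort their change

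*SAP*

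**What the plan says.** SAP 16.3 begins: "To adjust weight (kg) and height (cm) for sex and age, one needs to compare them to standard reference values". It points to external growth-chart tables and gives the LMS formula, in which "where X is the physical measurement (e.g. weight and height) and L, M and S are the values from the appropriate table" for the child's age in months and sex. It then adds: "X must be in metric measurements (kilograms or meters". It describes the reference quantities only in general terms: "parameters L, M, and S are the Box-Cox transformation power, median, and standard deviation, respectively, in the reference data". No value of L, M or S appears in either document, and the unit of M is not stated.

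The z-scores feed SAP 11.5.2, where "the change from baseline to Week 8 in the age-and-gender-adjusted height and weight will be analyzed using an ANOVA model with treatment as factor", with a Wilcoxon test alongside. Protocol 9.7.6.5.2 plans the same kind of analysis for height ("Weight and height will be presented as standardized z-scores adjusted for gender and age, using the lambda-mu-sigma method") and names no unit.

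**The concern.** Weight is in kilograms in both sentences, so it is consistent. Height is in centimetres in one sentence and metres in the other, and nothing elsewhere in the SAP or protocol settles which applies. The later sentence is the one phrased as a requirement on X, so it is the one a programmer would be expected to follow.

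The formula uses X only through X/M. If M is in centimetres, entering X in metres makes that ratio 100 times too small for every child. At stake is the height part of a planned safety analysis of growth in patients aged 7 to 17.

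**Working it through.** The documents report no z-score, so there is no figure to reproduce. The check applies the SAP's own formula with X in each unit.

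**Inputs from the documents**
- Formula (SAP 16.3): z = ((X/M)^L - 1)/(S·L) if L ≠ 0, and z = ln(X/M)/S if L = 0.
- L, M and S are looked up by age in months and sex (SAP 16.3).
- Height is measured only at Screening and Visit 8/ET (SAP Table 4-2). With a screening period of 1 week, extendable to 5, the two heights are nominally 1 + 8 = 9 weeks and at most about 5 + 8 = 13 weeks apart.

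**Assumptions, not in the documents**
- M is in centimetres (implied by the opening sentence of 16.3), with M = 140.
- S = 0.03, 0.045 or 0.06. At L = 1 these correspond to 4.2, 6.3 and 8.4 cm (S × 140).
- L between -1 and 2.

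**Step 1: child at the median.** With X = 140 cm, X/M = 1 and z = 0 for every L and S. With X = 1.40 m, X/M = 0.01. At L = 1:
- S = 0.03: (0.01 - 1)/0.03 = -33.0
- S = 0.045: (0.01 - 1)/0.045 = -22.0
- S = 0.06: (0.01 - 1)/0.06 = -16.5

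Over all L and S tried, z runs from -3300 (L = -1, S = 0.03) to -8.3 (L = 2, S = 0.06). No combination gives a credible value.

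**Step 2: separation between children.** At L = 1 and S = 0.045, heights of 125, 140 and 155 cm should give z = -2.38, 0 and +2.38. In metres they give -22.02, -22.00 and -21.98.

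**Step 3: change in z, with L, M and S fixed.** Replacing X by X/100 multiplies (X/M)^L by 100^(-L), and the constant -1 cancels in the difference. The change is therefore divided by 100^L. For growth from 140 to 141 cm with S = 0.045:

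| L | Change, X in cm | Change, X in m | Ratio cm/m |
|---|---|---|---|
| -1 | 0.1576 | 15.76 | 0.01 |
| 0 | 0.1582 | 0.1582 | 1 |
| 0.5 | 0.1584 | 0.0158 | 10 |
| 1 | 0.1587 | 0.0016 | 100 |
| 1.5 | 0.1590 | 0.00016 | 1000 |
| 2 | 0.1593 | 0.000016 | 10000 |

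**Step 4: change in z when the reference values move with age.** Assume height goes from 140 to 141 cm, M from 140 to 140.9 cm, and L = 1 and S = 0.045 at the first visit. The correct change is about (141/140.9 - 1)/0.045 = 0.016. In metres:
- S moves to 0.0452: (1.41/140.9 - 1)/0.0452 + 22.0 = +0.098
- S moves to 0.0448: -0.098
- L moves to 1.02: +0.41
- L moves to 0.98: -0.43

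The mechanism is that each child carries an offset of about -1/(S·L), here -22. A small movement in S or L shifts that offset by more than the true growth signal. If only M moves, the factor stays at 100^L.

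**The case against.** **The metre sentence may be loose wording.** Its main clause asks for metric measurements, and the parenthesis may be meant only to exclude inches and pounds. The section names centimetres first and sends the programmer to the table, where M's unit would be seen. This reading is possible, but it does not remove the contradiction, because the parenthesis names metres. If M turned out to be in metres, the opening sentence would be the one to correct.

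**The impossible values rest on M being in centimetres.** That is right. It is an inference from the opening sentence, and the table is not in the documents, so the result is stated conditionally.

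**The effect on the tests may be nil.** A reader might infer that the change in height z would always come out 100 times too small, sit near zero and so hide an effect on growth. The documents do not support that. The factor of 100 needs L = 1 with L and S the same at both visits. In that case every child's change is divided by the same 100, so the ANOVA F test and the Wilcoxon test are unchanged and only the displayed size is wrong. At L = 0, which the SAP formula allows, the change is not affected at all. If L or S moves with age, the change can be too large or have the wrong sign. No L values are given, so none of these cases can be singled out.

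**It would be caught.** Baseline height z-scores near -22 would probably be noticed on first output, and raw height and its change are summarised separately (SAP 11.3). This stands, and it keeps the matter minor. It does not make the written rule correct.

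**Conclusion.** SAP 16.3 contradicts itself on the unit of height, and the rule is wrong as written. If M is in centimetres, metres give impossible height z-scores at every L and S tried: -22 instead of 0 for a child at the median with L = 1 and S = 0.045, and from -3300 to -8.3 over L = -1 to 2 and S = 0.03 to 0.06. The change in height z, which is what SAP 11.5.2 tests, is divided by 100^L if L, M and S are fixed between visits. If L or S shifts with age, it is wrong by an unpredictable amount and possibly in sign.

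These sizes rest on assumed L, M and S and on the implied unit of M. The reach is narrow: only the height z-scores within the growth evaluation. Weight z-scores, raw height summaries, efficacy analyses and sample size are untouched. Severity is low: a worthwhile correction, likely to be caught in programming even if left.

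**What to change.** Replace the unit sentence in SAP 16.3 with: *X must be in the same unit as M in the reference table (kg for weight, cm for height).* Before finalising, confirm the unit of M in the table that will be used and adjust the parenthesis if it differs. The cost is one sentence in the SAP; no data collection or analysis method changes.
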